10.4 Data Analysis

Descriptive statistics, including mean, median, standard deviations and ranges for all continuous measures will be tabulated and reported. Percentages and frequencies for all categorical measures will also be presented. Time to events endpoints will be reported using Kaplan-Meier estimates, with 95% confidence intervals (CI) for median time to event.

All statistical analyses will be performed using SAS v9.3 or higher.

10.4.1 Demographics and Baseline Characteristics

Demographic and baseline disease characteristics will be summarized. Data to be tabulated will include demographic features such as age, sex and race, as well as disease-specific characteristics.

The number and percentages of patients enrolled, treated, completed the treatment/study and withdrawn from treatment/study for any reasons will be presented overall.

10.4.2 Efficacy Analysis

All efficacy analyses will be performed using the Efficacy Evaluable Population.

- Overall Response Rate (ORR) is defined as the proportion of patients with observed complete response (CR) or partial response (PR) according to the RECIST v1.1 criteria.
- Clinical Benefit Rate (CBR) is defined as the proportion of patients with CR, PR or SD x 6 months according to the RECIST v1.1 criteria.
 - For ORR and CBR, patients without a post-baseline tumor assessment will be classed as not evaluable (NE) and considered as non-responder.
- Progression Free Survival (PFS), defined as the time from the first day of study drug administration (Day 1) to disease progression (event) as defined by the RECIST v1.1 criteria, or death (event) on study. Patients who are alive and free from disease progression will be censored at the date of last tumor assessment. Patients who receive non-protocol therapy (subsequent therapy) prior to incurring an event will be censored at the date of last tumor assessment prior to the start of subsequent therapy. Patients who do not have a post-baseline tumor assessment will be censored at the date of first treatment (Day 1).
- Overall Survival (OS), defined as the time from the first day of study drug administration (Day 1) or death on study. Patients who are alive will be censored at the date of last known date alive.
- Duration of Response (DOR), is defined as the time from the first date of CR or PR to disease progression or death as defined by the RECIST v1.1 criteria. Patients who are alive and free from disease progression will be censored at the date of last tumor

CONFIDENTIAL

STUDY DRUG(S): EVEROLIMUS
FINAL PROTOCOL DATE: 19 JUNE 2014

SCRI INNOVATIONS STUDY NUMBER: BRE 212
VERSION 1.0

assessment. Patients who receive non-protocol therapy (subsequent therapy) prior to incurring an event will be censored at the date of last tumor assessment prior to the start of subsequent therapy. Only those patients who achieved CR or PR will be included in the summaries of DOR.

- Percentage of patients progression-free at 4 and 6 months, defined as the proportion of patients who are progression-free as defined by the RECIST v1.1 starting from the date of their first treatment.

For ORR and CBR, the estimates and the associated 95% CI (based on both asymptotic normal approximation and exact binomial methods) will be calculated.

Best overall response will be tabulated: CR, PR, SD, PD and not evaluable (NE).

For PFS, DOR and OS, Kaplan-Meier curves will be generated and the median time to event and the associated 95% CI will be provided.

The number and percentage of patients progression-free at 4 and 6 months will be provided.

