2.4 Secondary Endpoints

The secondary endpoints of this study are:

- Overall response rate in the subset of patients with measurable disease.
- Clinical benefit rate (Complete response (CR) + Partial response (PR) + Stable disease (SD) x 6 months).
- Duration of response (DOR).
- Percentage of patients progression-free at 4 and 6 months.
- Overall survival (OS).
- Safety and tolerability of everolimus with an anti-estrogen therapy.

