Anti-estrogen Therapy (tamoxifen, fulvestrant, anastrozole, letrozole, exemestane, toremifene, or LHRH agonist in conjunction with anti-estrogen therapy)

The patient will be prescribed the last anti-estrogen therapy to which they demonstrated disease progression. Anti-estrogen therapy (tamoxifen, fulvestrant, anastrozole, letrozole, exemestane, toremifene, or LHRH agonist in conjunction with anti-estrogen therapy) will be administered according to the directions in the FDA approved labeling. Consult the appropriate package insert for specific information and instructions.

Restaging

A treatment cycle will be defined as 4 weeks, with radiological evaluations every 2 cycles (8 weeks). Patients will be evaluated for response to treatment before every odd numbered cycle with imaging and chemistry. Patients will be treated until disease progression, toxicity requiring cessation of treatment or withdrawal of consent.

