 Clinical Benefit	 Complete Response + Partial Response + Stable Disease as best observed response  Complete Response + Partial Response (confirmed with weeks apart) + Stable Disease (at least weeks from start of treatment)  Other criteria, specify: (Complete response (CR) + Partial response (PR) + Stable disease (SD) x 6 months)																											
 Progression	Disease progression (event) as defined by the RECIST v1.1 or death on study; non-protocol therapy (subsequent therapy) prior to incurring an event will be censored at the date of last tumor assessment prior to the start of subsequent therapy																											
 Subsequent Therapy	Non-protocol therapy prior to incurring an event																											
 Treatment Failure	N/A																											

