Table 5	Treatment and Dose Modifications	Duration on Treatment (weeks), N, Mean, SD, Median, Min, Max Dose Reduction (n, %) None Patients with 1 Patients with 2 Patients with >= 3 Dose Interruption (n, %) None Patients with 1 Patients with 2 Patients with >= 3	Safety
Table 6	Measurable Lesions	Measurable Lesions (n, %) Non-Measurable Lesions (n, %) Evaluable Bone Only Disease (n, %)	Enrolled Patients
Table 7	Best Overall Response	Best overall response (n, %): Complete response (CR), Partial response (PR), Stable disease (SD), NonCR/NonPD, Progressive disease (PD), Not evaluable (NE), Not applicable (N/A) Missing Objective Response Rate (ORR) (= CR+PR): ORR, 95% Confidence interval Clopper-Pearson	Efficacy Evaluable, Safety

Standard TFLs			
Table No	Description	Variables/Analyses To Be Included	Population
		Normal Approximation Clinical Benefit Rate (CBR) $(=CR+PR+SD \geq 4 \text{ months})$: CBR, 95% Confidence interval Clopper-Pearson Normal Approximation Clinical Benefit Rate (CBR) $(=CR+PR+SD \geq 6 \text{ months})$: CBR, 95% Confidence interval Clopper-Pearson Normal Approximation]	
Table 8	Progression-free Survival (Kaplan-Meier estimates & 95% CI)	Number of patients with events, Number of patients censored, Median Progression-free Survival [months (95% CI)] 25% Percentile Follow-up [months (95% CI)] 75% Percentile Follow-up [months (95% CI)] Progression-free Survival Estimates [probability, (95% CI)]: 4 months, 6 months, 12 months	Efficacy Evaluable, Safety
Table 9	Overall Survival (Kaplan-Meier estimates & 95% CI)	Number of patients with events, Number of patients censored, Median Overall Survival [months (95% CI)] 25% Percentile Follow-up [months (95% CI)] 75% Percentile Follow-up [months (95% CI)] Overall Survival Estimates [probability, (95% CI)]: 4 months, 6 months, 12 months	Efficacy Evaluable, Safety
Table 10	Adverse Event Overview	Any Adverse Event Treatment-related Adverse Event Everolimus-related Adverse Event Anti-Estrogen Therapy-related Adverse Event Serious Adverse Event Treatment-related Serious Adverse Event Serious Adverse Event leading to Death Treatment-related Serious Adverse Event leading to Death Adverse Events leading to Treatment Discontinuation Adverse Events leading to Treatment Interruption Adverse Events leading to Treatment Reduced	Safety

Standard TFLs			
Table No	Description	Variables/Analyses To Be Included	Population

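### Read literally, SAP Table 7 leaves stable non-measurable disease (NonCR/NonPD) out of the clinical benefit rate, and no rule says how stable disease is counted to 4 or 6 months when scans are 8 weeks apart

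*Protocol*

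**What the plan says.** Protocol 2.4 lists CBR as a secondary endpoint, with a stability component of "Stable disease (SD) x 6 months". Protocol 10.4.2 defines it as "the proportion of patients with CR, PR or SD x 6 months according to the RECIST v1.1 criteria". SAP 1.2 repeats this, and SAP Section 4 enters it as free text: "Complete response (CR) + Partial response (PR) + Stable disease (SD) x 6 months". The form's preset alternative, "Stable Disease (at least weeks from start of treatment", is unticked and its number of weeks is blank. SAP Table 7 turns the criterion into SD of at least 6 months and adds a second CBR row at 4 months or more.

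The best-response categories in Table 7 include "Stable disease (SD), NonCR/NonPD, Progressive disease (PD", so NonCR/NonPD stands apart from SD. The lists in protocol 10.4.2 and SAP 1.2 have only CR, PR, SD, PD and NE.

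On timing, the Restaging text in protocol 5.1 says: "A treatment cycle will be defined as 4 weeks, with radiological evaluations every 2 cycles (8 weeks". Protocol 7.4 and Appendix D note j place the scans before odd-numbered cycles, starting with Cycle 3. Protocol 7.6.1 moves patients who stop treatment before progression to visits every 3 months, plus or minus 1 month.

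**The concern.** There are two gaps in one endpoint.

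The first is classification. Inclusion criterion 7 admits patients with lytic or mixed bone lesions and no measurable disease. Protocol 2.4 limits the response rate to patients with measurable disease but puts no such limit on CBR, so these patients are in the CBR denominator. If their stable status is coded NonCR/NonPD and Table 7 adds only CR, PR and SD, lasting stability earns them nothing.

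The second is timing. No restaging is scheduled at 4 or 6 months, and neither document gives a start date, end date or scan window for SD duration. A patient stable at week 24 and progressing at week 32 is a clinical benefit under some readings and not under another. The trial is open-label with a single arm, so a rule left open until programming can be chosen with the results in view.

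**Working it through.** **Inputs.** Scans at weeks 8, 16, 24 and 32 (protocol 5.1, 7.4, Appendix D). Median PFS of 2.8 months (null), 5 months (alternative) and 6.9 months (cited result), and N = 42 (protocol 10.2). Assumptions not in the documents: exponential PFS, and a response rate of 10-20%.

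**1. The plan's own figure.** The documents give no expected CBR, so the only design figure to reproduce is N = 42. Testing PFS at the null median, S0 = 0.5 and S1 = 0.5^(2.8/5) = 0.6783. With variance under the alternative, n = (1.6449 + 0.8416)² × 0.6783 × 0.3217 / 0.1783² = 42.4, and power at 42 is 79.6%. The sample size therefore rests on the 2.8- and 5-month medians; CBR plays no part in it.

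**2. NonCR/NonPD, texts side by side.**
- Appendix E labels persistence of non-target lesions SD. Its overall-response table has no NonCR/NonPD outcome, and no row for a patient without target lesions.
- Protocol 10.4.2 and SAP 1.2 have no NonCR/NonPD category, so SD is their only label for stability.
- SAP Table 7 separates the two labels, and both of its CBR rows add only CR, PR and SD. SAP Table 6 counts bone-only patients, so the plan expects some.

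Each stable patient left out costs 1/42 = 2.4 points. If a share f of patients has no measurable disease and the same PFS as the rest, the loss is f × 46.5 points at the 5-month median (step 5, ignoring responders). The documents do not give f, so I put no total on this part.

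**3. Scan calendar.** Months = weeks × 7 / 30.4375, which gives 1.84, 3.68, 5.52 and 7.36 months for weeks 8, 16, 24 and 32. Six months is 26.1 weeks.

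**4. Readings for SD at week 24 and PD at week 32.**
- Week 24 is accepted as 6 months: qualifies.
- SD runs to the PD date (7.36 months): qualifies.
- An SD scan at or after 6 months is needed: does not qualify.

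**5. Size at 6 months.** S(t) = 0.5^(t/median), ignoring responders.

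| Median PFS | Week 24 counts | Week 32 needed | Gap |
|---|---|---|---|
| 2.8 months | 25.5% | 16.2% | 9.3 points |
| 5 months | 46.5% | 36.1% | 10.5 points |
| 6.9 months | 57.4% | 47.7% | 9.7 points |

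Gaps are taken before rounding. At 5 months, 42 × 0.105 = 4.4 patients.

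**6. Responders.** CR and PR count under every reading. With a response rate r independent of PFS, the gap is (1 − r) × 10.5 points: 9.4 at r = 10% and 8.4 at r = 20%. A simulation on the 8-week grid, with responders drawn from patients having at least one non-PD scan, gives 50.5% against 41.4% (9.1 points) and 54.4% against 46.7% (7.7 points).

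**7. The 4-month row.** Accepting week 16 (3.68 months) gives 60.0% at the 5-month median; needing week 24 gives 46.5%. The gap is 13.5 points, again ignoring responders.

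**The case against.** CBR is descriptive: it has no null value, test or decision rule. Kaplan-Meier PFS at 4 and 6 months with confidence intervals is already planned, and it describes disease control without any SD-counting rule. That stands, and it limits the weight of the point.

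Two of the three readings in step 4 agree. PFS and duration of response both run to the progression date, and the SAP ticks first treatment as the start date for its endpoints, so by analogy the week-24 patient qualifies. Reading 6 months as six 4-week cycles is also natural. This is persuasive as a guess at intent, but neither document says it, Table 7 writes the threshold as at least 6 calendar months, and patients censored soon after week 24 stay ambiguous.

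On NonCR/NonPD, the separate line may be only for display, and nothing expressly excludes these patients. That too is fair: the exclusion follows from reading the Table 7 formula literally, and Appendix E points the other way. A programmer working from the table would still have no instruction to combine the two.

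A reader might also infer that CBR loses comparability with the 42%, 61% and 55% rates in protocol 1.2. The documents do not support that. Those rates are background, not benchmarks, and the definitions behind them are not given.

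**Conclusion.** The point holds as a specification gap in a secondary endpoint. Table 7, followed literally, denies clinical benefit through stability to patients without measurable disease and conflicts with Appendix E. The effect is 2.4 points of CBR per affected patient out of 42; the number affected cannot be known from the documents.

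The timing gap is worth up to about 10 points at the 5-month median, and about 8 to 9 points with an assumed response rate of 10-20%. These figures assume exponential PFS and scans on schedule.

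A reader might infer that a patient stable at week 24 fails the criterion, or that CBR will come out 10 points low. Neither follows: failure arises only if an SD scan at or after 6 months is demanded, and the full 10 points requires that there be no responders. Nor does the gap reach the primary endpoint. The PFS analysis and N = 42 do not use CBR.

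**What to change.** Amend protocol 2.4 and 10.4.2 and SAP Section 4 and Table 7, and align SAP 1.2, as follows.

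- Count NonCR/NonPD with SD for CBR.
- State that SD duration runs from first treatment, and that a patient qualifies if a tumor assessment at the scheduled week-24 restaging or later, within a stated window, shows no progression.
- Apply the same rule at week 16 to the 4-month row.
- State how CBR handles patients who stop treatment before progression and move to 3-monthly visits, since their scans leave the 8-week grid.

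The cost is wording only; no scans, visits or patients are added. The downside is that the nominal thresholds become 24 weeks (5.5 months) instead of 6.0 months and 16 weeks (3.7 months) instead of 4.0 months, which the report should state.

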10.4.3 Safety Analysis

Safety will be assessed through the analysis of the reported incidence of treatment-emergent AEs. Treatment-emergent AEs are those with an onset on or after the initiation of therapy, and will be graded according to NCI CTCAE v 4.03. A copy of CTCAE scoring system may be downloaded from: http://evs.nci.nih.gov/ftp1/CTCAE/CTCAE_4.03_2010-06-14_QuickReference_8.5x11.pdf.

The AEs will be coded using Medical Dictionary for Regulatory Activities (MedDRA), and summarized using system organ class and preferred term for all patients in the Safety Population. In addition, summaries of SAEs, AEs leading to treatment discontinuation, AEs by maximum NCI CTCAE grade, and AEs related to study treatment will also be presented.

Other safety endpoints including laboratory results, vital signs and ECG findings will be summarized for all patients in the Safety Population.

10.4.4 Pharmacokinetics/Pharmacodynamics

PK/PD analyses will not be provided for this study.

10.5 Analysis Time Points

10.5.1 Final Analysis

The final analysis of the study will occur when 42 patients have discontinued treatment, progressed, died or are still on treatment but have at least 12 months of follow up (time from first treatment until last tumor assessment).

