Study Chair Signature

July 31, 2014
Date

Study Chair
[name].
Sarah Cannon Research Institute

[name]

6 August 2014

SCRI Development Innovations, LLC
[name], Director

SCRI Development Innovations, LLC
Representative Signature

Date

STUDY DRUG(S): EVEROLIMUS
FINAL PROTOCOL DATE: 19 JUNE 2014

CONFIDENTIAL

SCRI INNOVATIONS STUDY NUMBER: BRE 212
VERSION 1.0

Clinical Study Principal Investigator Signature Form

A Phase II Open Label Study of Everolimus in Combination with Anti-estrogen Therapy in Hormone Receptor-Positive HER2-Negative Advanced Breast Cancer

SCRI INNOVATIONS STUDY NUMBER: BRE 212

DATE FINAL: 19 June 2014

By signing this protocol acceptance page, I confirm I have read, understand, and agree to conduct the study in accordance with the current protocol.

Principal Investigator Name
(Please Print)

Principal Investigator Signature

Date

Please retain a copy of this page for your study files and return the original signed and dated form to:

SCRI Development Innovations, LLC
[name]
Attn: BRE 212 Study Team
[name]

CONFIDENTIAL

STUDY DRUG(S): EVEROLIMUS
FINAL PROTOCOL DATE: 19 JUNE 2014

SCRI INNOVATIONS STUDY NUMBER: BRE 212
VERSION 1.0

BRE 212 PROTOCOL SYNOPSIS

Title of Study:	A Phase II Open Label Study of Everolimus in Combination with Anti-estrogen Therapy in Hormone Receptor-Positive HER2-Negative Advanced Breast Cancer	
SCRI Innovations Study Number:	BRE 212	
Sponsor:	SCRI Development Innovations, LLC – Nashville - TN	
Study Duration:	The duration of the study is approximately 30 months (enrollment + treatment)	Phase of Study: II
Study Centers:	This study will be conducted by 9 participating sites.	
Number of Patients:	46 patients will be enrolled in the study.	

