10.2 Sample Size Considerations

Results from the recently published BOLERO-2 study reported a median PFS of 2.8 months (as assessed by the treating investigator) that improved to 6.9 months as a result of the addition of everolimus in patients treated with exemestane after failing the NSAI therapy (Baselga J. et al. 2012). A similar median PFS is predicted in this study’s patient population that is based on similar inclusion criteria. It is anticipated that everolimus in combination with the last anti-estrogen therapy on which the patient demonstrated disease progression, will result in an increase in median PFS from 2.8 months to 5 months in this refractory population.

Based on the above assumptions, given a follow-up period of 12 months after the completion of enrollment (18 months), with a 5% alpha and a one-sided test of hypothesis, a sample size of 42 will provide 80% power to detect an improvement in median PFS from 2.8 months to 5 months in the patients treated with the combination of everolimus with anti-estrogen therapy. Allowing for 8-10% inevaluable patients, the total number of patients to be enrolled is 46 patients.

Sample size calculations are based on SWOGSTAT online sample size calculator for one-arm non-parametric survival endpoints (http://www.swogstat.org/stat/public/one_nonparametric_survival.htm).

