1.4 Timing of Analysis	
Planned Interim Analysis	 Cohort Review / Dose Escalation  Safety Review  Interim Efficacy/Safety Analysis  Independent DMC/DSMB  Annual Report / Investigator Brochure (IB)  Abstract / Scientific Presentation (Oral/Poster)
Final Analysis	The final analysis will occur when 42 patients have discontinued treatment, progressed, died or are still on treatment but have at least 12 months of follow-up (time from first treatment until last tumor assessment).

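### The final-analysis trigger does not deliver the 12 months of post-enrollment follow-up that Section 10.2 assumes

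*Protocol*

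**What the plan says.** Protocol Section 10.2 states the sample size "given a follow-up period of 12 months after the completion of enrollment (18 months"). It plans "with a 5% alpha and a one-sided test of hypothesis" and says that "a sample size of 42 will provide 80% power to detect an improvement in median PFS from 2.8 months to 5 months". It then adds an allowance: "Allowing for 8-10% inevaluable patients, the total number of patients to be enrolled is 46 patients". Eighteen months plus twelve is month 30, in line with the Synopsis: "The duration of the study is approximately 30 months (enrollment + treatment").

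Section 10.5.1 fixes the analysis date differently: "The final analysis of the study will occur when 42 patients have discontinued treatment, progressed, died or are still on treatment", the on-treatment group needing at least 12 months from first treatment to last tumor assessment. SAP 1.4 carries the same rule: "The final analysis will occur when 42 patients have discontinued treatment, progressed, died or are still on treatment". Neither says that the 42 must belong to the Efficacy Evaluable Population of Section 10.3, which requires one cycle of treatment and a post-baseline assessment.

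Section 7.6.1 keeps following patients who stop treatment without progression, every 3 months, until progression or 3 years from the start of treatment.

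**The concern.** The sample-size section and the analysis-timing section describe two different cut-offs. The trigger is met once all but four of the 46 enrolled patients have qualified, and most qualify well before 12 months. Progressions and deaths count on the day they happen. So does a treatment stop without progression, although Section 7.6.1 goes on following that patient. A patient lost in Cycle 1 also counts, although Section 10.3 leaves that patient out of the efficacy set.

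What is at stake is the maturity of the later estimates. SAP Tables 8 and 9 ask for PFS and OS at 12 months, and Table 16 for duration of response. CBR is a simple proportion that needs stable disease for 6 months, so a patient still stable with a shorter record at the cut-off cannot yet qualify.

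**Working it through.** **Inputs from the documents.** 46 enrolled; 42 required; 18 months of accrual; 12 months of follow-up; median PFS 2.8 (null) and 5 (alternative) months, with 6.9 months (the cited trial's result) as a sensitivity; scans every 8 weeks. **Assumed.** Even accrual, exponential PFS, four patients lost early as non-evaluable (46 − 42), and treatment stops without progression at 0 to 0.05 per month.

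**1. The plan's own figure.** Section 10.2 used a calculator for "one-arm non-parametric survival endpoints". Testing PFS at 2.8 months:

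- S0 = 0.500; S1 = 0.5^(2.8/5) = 0.678.
- n = (1.645 + 0.842)² × 0.678 × 0.322 / (0.678 − 0.500)² = 42.4. Power at n = 42 is 79.6%.
- Inflation: 42/0.92 = 45.7, i.e. 46; 42/0.90 = 46.7, i.e. 47.

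So 42 and 46 are reproduced closely. In this form the test needs only 2.8 months of follow-up per patient.

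**2. Trigger date by hand.** With no treatment stops and every patient evaluable, the expected number not yet counted at month t (18 ≤ t ≤ 30) is

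U(t) = (46/18) × (5/ln 2) × [0.5^((t−18)/5) − 0.5^(12/5)].

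At t = 24: 2.556 × 7.213 × (0.435 − 0.189) = 4.5. The number outstanding therefore drops from 5 to 4, and the trigger fires, at about month 24.

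**3. Trigger date by simulation.** Each patient counts at entry + min(PFS, treatment stop, 12 months); the trigger is the 42nd count. PFS is in continuous time except where scans are named.

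| Rule and assumptions | Median trigger (month) | Months before 30 |
|---|---|---|
| Any 42 of 46, median 5, no stops, all evaluable | 23.9 (5-95%: 21.4-26.3) | 6.1 |
| Same, progression seen only at 8-week scans | 24.5 | 5.5 |
| Any 42, four early non-evaluable patients counted | 23.5 | 6.5 |
| Same, stops at 0.02 per month | 22.9 | 7.1 |
| Same, stops at 0.05 per month | 22.0 | 8.0 |
| Any 42, no stops, all evaluable, median 6.9 | 25.4 | 4.6 |
| Any 42, no stops, all evaluable, median 2.8 | 20.8 | 9.2 |
| 42 Efficacy Evaluable, median 5, no stops | 28.6 | 1.4 |
| 42 Efficacy Evaluable, median 5, stops at 0.05 | 27.8 | 2.2 |

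With 8-week scans, early losses and moderate stop rates (0 to 0.035 per month) together, the trigger falls at about month 23.0 to 24.5. Treatment stops move it by 23.5 − 22.9 = 0.6 to 23.5 − 22.0 = 1.5 months.

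**4. Follow-up at the trigger.** With even accrual, the share of patients who could have 12 months is (t − 12)/18: (23.0 − 12)/18 = 61% and (24.5 − 12)/18 = 69%. Simulation gives up to 70%, and about 5.4 to 6.9 months for the last patient, against 12 assumed.

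**5. Effect on PFS.** With four non-evaluable patients and a 5-month median:

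- No stops: about 35 PFS events among evaluable patients at the trigger, against 39 at month 30.
- Stops at 0.05 per month, censored at the stop: 27 against 30. If progression after a stop is still counted: 33 against 39.
- Simulated power of the Kaplan-Meier test at 2.8 months (no stops): 75.2% at both dates. The shortfall from 80% is present at month 30 too, so the trigger does not cause it.

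**6. Effect on CBR.** About 1 to 2 patients are still on treatment with a last scan before 6 months at the 5-month median, and about 3 if the true median is 2.8 months.

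**The case against.** The strongest reply concerns the meaning of 42. Section 10.2 uses that number for the evaluable target, with 46 enrolled to protect it, so 42 in Section 10.5.1 may mean those same patients. The trigger is then only about 1.5 to 2 months early at a 5-month median (about 3.5 at 2.8 months with no stops). This is a fair reading, but the text does not state it, and the two readings differ by about 5 months.

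It can also be said that the primary endpoint is safe, and that stands. Under the literal reading only four patients are unresolved at the cut-off, and Kaplan-Meier censoring handles them. The SAP's PFS table censors a treatment stop at the last evaluable assessment, so counting the stop as resolved agrees with that table, though not with the continued follow-up in Section 7.6.1.

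Several stronger inferences are tempting and are not supported:

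- **That treatment stops and non-evaluable patients cause the gap.** It is already 6.1 months with neither. Most of it comes from needing only 42 of 46 and counting events as they occur.
- **That the 42 evaluable patients behind the power are lost.** The trigger sets the date, not the analysis set; all qualifying patients among the 46 can be analyzed.
- **That OS would be mature at month 30.** Neither document gives a median OS. With an assumed 28 months, there would be 13-14 deaths at the trigger and about 18 at month 30, and 18/46 = 39% is still immature. Survival follow-up runs to 3 years, but no later OS analysis is described.
- **That CBR is badly distorted.** The effect is 1 to 2 patients at the design alternative. The documents give an explicit non-responder rule only for patients without a post-baseline assessment.

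**Conclusion.** The mismatch is on the face of the documents and should be corrected. Read literally, the trigger precedes month 30 by about 5.5 to 7 months at a 5-month median with 8-week scans; about 61-70% of patients then have 12 months of potential follow-up, and about 3 to 4 fewer PFS events are seen (about 6 fewer with frequent stops whose later progressions count). If the 42 are Efficacy Evaluable, the gap is about 1.5 to 2 months.

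The cost is precision in 12-month PFS and OS and in duration of response, and to a small degree CBR. A reader might conclude that the primary analysis is underpowered or invalid because of the trigger; the calculations show no such effect. The timing figures rest on even accrual, exponential PFS and assumed stop rates, none of which the documents give. The conflict between Sections 10.2 and 10.5.1 does not depend on them.

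**What to change.** In Protocol 10.5.1 and SAP 1.4, set the final data cut-off at 12 months after the last patient's first dose, or earlier if every treated patient has had a PFS event or left follow-up.

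Smaller edits do not reach month 30. Ceasing to count treatment stops, with any 42 still sufficient, leaves the trigger at month 23.5 to 23.9. Requiring 42 Efficacy Evaluable patients gives 27.8 to 28.6, and requiring all 46 gives 28.8. If the sponsor prefers an earlier read-out, state that the 42 are Efficacy Evaluable patients and restate in 10.2 the follow-up that this delivers.

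The cost is one sentence in each document and a final report up to about 6 to 7 months later than under the current trigger. No patients or visits are added, and the cut-off stays within the stated 30 months if enrollment takes 18.
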